17 ETHICAL AND REGULATORY CONSIDERATIONS

17.1 Regulation statement

This trial will be conducted according to the principles of the declaration of Helsinki (Fortaleza October 2013) and in accordance with the Medical Research Involving Human Subjects Act (WMO) and other European guidelines, regulations and acts. Data management, monitoring and reporting of the study will be carried out in accordance with the ICH GCP guidelines.

The trial must be approved by the appropriate ethics committee of each participating institution prior to its entry into the study. Eligible patients should be informed in person by the treating surgeon and receive written information about the trial in their own language. Informed consent should be obtained from each patient according to the guidelines of the local ethical committee, prior to randomisation into the study. Patients remain free to withdraw at will at any time from the study without giving reasons.

17.2 Recruitment and consent

The informed consent procedure should be performed by the treating physician or a representative that is aware of the details and complications of both treatments included in the trial. Therefore, it is the trial's preference that the consent is taken by the treating physician.

The information offered to the patient or representative contains:

- A statement that the trial involves research
- A full and fair explanation of the procedures to be followed
- A full explanation of the nature, expected duration, and purpose of the study
- A description of any reasonable foreseeable risks or discomfort to the patient
- A description of any benefits which may reasonably be expected
- A statement that patient data will be handled with care and confidentiality and the period of time the data is saved (15 years)
- A statement that patient bodily material is being stored for 15 years
- A statement that participation is voluntary, that refusal to participate will involve no penalty or loss of benefits to which the patient is otherwise entitled, and that the patient may discontinue participation at any time without penalty or loss of benefits, in which case the patient will receive standard treatment with the same degree of care.
- Patients are given a minimum of 72 hours to decide whether or not to participate in the study

17.3 Objection by minors or incapacitated subjects (if applicable)

Minors and legally incompetent adults are excluded from the trial.

17.4 Benefits and risks assessment

The potential benefit resulting from participation is improvement in oncological outcome and prevention from a permanent colostomy in the experimental arm. Patients in the experimental arm will be closely monitored with frequent follow-up visits. Because an extensive quality assurance program is integrated in the trial, the risk for surgical-related complications will be relatively low. Previous large cohort series have shown that the procedure is safe and has potential benefits. Nevertheless a Data Safety Monitoring Board will evaluate safety during the trial.

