Main Exclusion criteria	T4 tumour and T3 with MRF involvement on MRI (after neoadjuvant therapy) Ingrowth in anal sphincter complex or m. levator requiring abdominoperineal resection Previous rectal resection (excl local excision), prostatectomy	
Intervention	Rectal resection by transanal TME with laparoscopic surgery	
Control arm	Rectal resection by laparoscopic TME	
Quality assurance	
The technical performance of TaTME will be standardised, including mandatory surgical steps and quality.
 
An operation manual and notes will be written based on the standardisation to monitor compliance.
 
Before entering the trial, all centres will have peer reviewed established procedure competence by assessment of unedited videos of three consecutive cases (2 TaTME + 1 laparoscopic TME).
 
All surgical procedural videos are kept within patient record information database electronically.
 
The videos will be evaluated using CAT. This competency assessment tool (CAT) is developed to evaluate the performance of TaTME.
 
All MRI and pathology data will be centrally reviewed.
	
Translational research	Blood and tissue from the primary tumour will be collected in specific centres and used for translational research on prognostic and predictive factors.	
	Outcome	Measurement
Primary	Local recurrence at 3 years	Event of local recurrence at 3 year follow-up
Secondary	
 • Quality of specimen • Involved Circumferential Resection Margin (CRM) • Morbidity and mortality • Residual mesorectum • • Disease-free and overall survival • Sphincter saving procedure • Functional outcome • Health related Quality of Life 	
 • Quality assessment by 'Quirke' • Clavien Dindo, 30 & 90 days • Postoperative MRI 3 year • MRI, pathology • Follow-up regimen • Colostomy percentage 1 year • LARS score • EORTC QLQ-29 and 30, EQ 5-D

Planned Sample Size	1104 patients in total; 735 in the TaTME arm and 369 in the laparoscopic TME arm to demonstrate a non-inferior effect on local recurrence of 4% after 3 years between the control group and the TaTME group. (Power 80% with a one-sided level of significance of 2.5%, dropout of 5%)
Planned Trial Period for inclusion	Four years (20+ centres, multinational)
Total duration of trial – report primary outcome	Inclusion period; three years Primary outcome at six years 5 year follow up at eight years

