4 TRIAL DESIGN

The study is an international, randomised, non-inferior, multicentre trial comparing traditional and transanal laparoscopic TME as the surgical treatment for rectal cancer. Patients will be accrued by all participating hospitals participating in the COLOR III study group (list of participating hospitals can be obtained through rectalcancersurgery.eu → 'COLOR III Trial'). All centres will follow a quality assurance program of the procedure itself and the data before data will be entered in the COLOR III trial. The COLOR III study group is an international group of surgeons with interest and expertise in minimally invasive colorectal surgery.

The first COLOR study started in 1997 and completed a large RCT in 2003 comparing laparoscopic to open surgery for colon cancer.^{36,37} Hereafter, many centres of this study group joined the COLOR II study group. The COLOR II study group recently completed a major RCT comparing laparoscopic to open TME in the treatment of rectal cancer.

The design involves allocation of all appropriate consecutive patients with mid or low rectum carcinoma to either of the two procedures at a randomisation ratio of 2:1 in favour of the TaTME procedure. Once eligibility has been established and patient details have been noted, the patient will be allocated to either transanal or laparoscopic TME. Assignment to one the two treatment groups will not be blinded. Randomisation will be performed by computer and will be balanced by T-stage, preoperative radiotherapy, height of the tumour, BMI and gender. Data will be analysed on 'intention to treat' basis in case patients are not subjected to the randomised treatment modality. Randomisation will be done through internet: rectalcancersurgery.eu (click 'COLOR III Trial → Professionals').

Included surgical procedures to obtain TME are 1. low anterior resection (LAR) with colorectal anastomosis 2. LAR with coloanal anastomosis

Excluded surgical procedures are extralevator abdominoperineal excision (ELAP) (i.e. patients with tumour in growth (more than 1/3) in the anal sphincter complex or levator ani.

Exclusion criteria are T4 tumours, T3 tumours with a suspected involved CRM after neoadjuvant therapy, patients with concomitant metastases or other malignancies, with malignancies in their medical history or with signs of acute mechanical obstruction by the tumour.

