12 FOLLOW-UP

12.1 Follow-up visits

According to the international guidelines (ASCO, NICE) patients participating in the COLOR III trial are asked to visit the outpatient clinic yearly for a period of 5 years. More frequent visits and additional examination are only on indication or to the preference of the attending surgeon. A chest radiograph and a liver ultrasound or CT-thorax/abdomen are performed to assess development of distant metastases according to international guidelines. Follow-up of patients with recurrent disease should continue until at least 3 years after detection of recurrence or until death.

A CT or MRI of the pelvis must be performed three years postoperatively to assess possible local recurrence and/or residual mesorectum. In case of suspicion of recurrence on CT-abdomen a pelvic MRI is mandatory. In the NICE guidelines a minimum of two CTs of chest, abdomen and pelvis in the first 3 years is needed in the regular surveillance. The ASCO states that CT imaging of these regions is even needed annually in high risk patients. Since mid and low rectal cancer is associated with high recurrence rate and therefore patients should be marked as high risk patients compared to patients with a high rectal cancer and imaging of the pelvis after three years is considered standard of care.

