12.3 Questionnaires

To measure quality of life and functional outcomes, several questionnaires will be used. These questionnaires will be sent by email and access to an anonymized webtool (Castor) will be granted, if the patient does not have an email account, the questionnaires will be sent to the patients' home addresses, accompanied by a return envelope provided with postage stamps and the address of the hospital.

The following questionnaires will be used:

EQ 5D-5L (Euroqol): This questionnaire is a simple, generic instrument for describing and valuing health related quality of life. It includes 5 items (mobility, personal care, daily activities, pain, and anxiety-depression) that are answered on a 3-point scale ranging from no problems (level 1) to extreme problems (level 3).

Global quality of life (EORTC-QLQ-C30-QL2): This sub questionnaire contains the 2 items of the global quality of life dimension of the EORTC-QLQ-C30 questionnaire.

Global quality of life (EORTC-QLQ-CR29): This questionnaire is developed to assess the quality of life in colorectal patients.

LARS-score: Five questions (with at least one question representing each of the four known LARS symptom categories, namely incontinence, frequency, urgency and emptying difficulties) showing the highest prevalence and impact on QOL were identified.

Functional outcome and HRQoL after therapy will be measured using these validated questionnaires at admission and at 3, 6, 12, 24 and 36 months post-operatively.

	1 month	3 months	6 months	9 months	12 months	18 months	24 months	36 months	48 months	60 months
Clinical evaluation		X	X	X	X	X	X	X	X	X
CEA		X	X	X	X	X	X	X	X	X
Colonoscopy					X				X	
CT-thorax/abdomen or CXR and ultrasound liver			X		X	X	X	X	X	X
MRI-pelvis or CT-pelvis								X		
Functional outcome and HrQoL	X	X	X		X		X	X		

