13.1 Definitions of recurrent disease

Evidence of recurrent disease is accepted when one of the following criteria is present:

- Local macroscopic tumour assessed by colono- or proctoscopy, (PET-)CT-scan or MRI of the pelvis
- Liver metastases on ultrasound, (PET-)CT-scan or MRI
- Lung metastases on chest radiography, (PET-)CT-scan or MRI
- Bone metastases on radiography, (PET-)CT-scan, MRI or bone scintigraphy
- Death with rectal cancer

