13.2 Definitions of local recurrence

- Cancer recurrence in the pelvic or perineal area
- Positive (PET-)CT-scan or MRI (high resolution with T2 weighted imaging)
- Positive histology or cytology of adenocarcinoma

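### One sentence ties frequent follow-up to the experimental arm alone, the follow-up chapter gives two visit schedules, and the local recurrence criteria have no combining rule, so detection of the primary event could depend on arm

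*Protocol*

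**What the plan says.** The primary endpoint (section 3.2) is the percentage of patients with local recurrence after three years. The following places bear on how it is detected.

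- **Section 17.4**, in the benefit-risk paragraph: "Patients in the experimental arm will be closely monitored with frequent follow-up visits". Nothing comparable is said of the laparoscopic arm.
- **Section 12.1**, for all trial patients: they "are asked to visit the outpatient clinic yearly for a period of 5 years". It adds: "More frequent visits and additional examination are only on indication or to the preference of the attending surgeon". It also requires a pelvic CT or MRI at three years in every patient, and a pelvic MRI when an abdominal CT raises suspicion of recurrence.
- **Section 12.3**, schedule table: the row "Clinical evaluation" is marked at 3, 6, 9, 12, 18, 24, 36, 48 and 60 months, with no split by arm. Pelvic imaging is marked only at 36 months.
- **Trial summary**, Follow-up: visits at least once a year.
- **Section 4**: "Assignment to one the two treatment groups will not be blinded".
- **Section 13.1**, recurrent disease in general: "Evidence of recurrent disease is accepted when one of the following criteria is present".
- **Section 13.2**, local recurrence: three items (pelvic or perineal site; positive scan; positive histology or cytology) with no word saying whether they are alternatives or all required.
- **Synopsis**, Quality assurance: "All MRI and pathology data will be centrally reviewed". The protocol does not state what part this review plays in the primary endpoint or whether the reviewers are masked.
- **Section 14.2**: local recurrence is to be compared by log-rank test.

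**The concern.** A comparison of recurrence rates is fair only if recurrences are looked for in the same way in both arms. Elsewhere the protocol asks for equality explicitly: preoperative care (6.3), anaesthesia (6.4), postoperative care (11.1) and treatment of recurrence (13.3). Section 12 has no such statement for follow-up, and the one sentence that mentions an arm, in 17.4, mentions only the experimental arm. Because the surgeon knows the allocation and may add examinations by preference, a site following these passages as written could examine the two arms with different intensity.

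The definition adds a second route. If one site accepts a positive scan and another waits for tissue, the same patient is an event in one place and not in the other, and that choice is made with the allocation known.

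At stake is a difference judged against a 4-point margin on a 5% event. Closer examination of the TaTME arm would count against non-inferiority. Fewer recurrences found or called in that arm would count towards it.

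**Working it through.** **Visits by month 36.** Section 12.1 gives 12, 24 and 36 months, which is 3. The 12.3 table gives 3, 6, 9, 12, 18, 24 and 36 months, which is 7. The summary sets a minimum of one a year, with which both are compatible, but 12.1 limits anything beyond yearly to indication or surgeon preference, and the table does not.

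**The two definitions.** 13.1 says one criterion is enough, and its local item can be met by endoscopy or pelvic imaging. 13.2 has no such rule and does not list endoscopy. Section 3.3 defines local recurrence (at five years) by site alone. The open question is whether imaging alone suffices or tissue is also needed.

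**The plan's own sample size.** Inputs from section 14.1 and the summary: 5% in both arms, margin 4 points, one-sided 2.5%, power 80%, ratio 2:1, loss 5%.

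Control n = (1.960 + 0.842)² × (0.05×0.95 + 0.05×0.95/2) / 0.04² = 349.5, so 350. TaTME is 700 and the total 1050. Then 1050/0.95 = 1105.3, so 1106, against 1104 stated. The figure reproduces.

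**Evaluable patients and events.** 369 × 0.95 ≈ 351 and 735 × 0.95 ≈ 698. At 5% that is about 18 control and 35 TaTME events, about 53 in all. For all 1104 randomised, 1104 × 0.05 ≈ 55.

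**Illustration.** The detection fractions are assumptions; the documents give none. Observed rate = true rate × detection fraction, and

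P(non-inferiority) = Φ[(0.04 − (pT − pC))/SE − 1.96], with SE² = pC(1 − pC)/351 + pT(1 − pT)/698.

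True rates 5% in both arms, full detection in TaTME:

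| Control detection | Observed pC | Spurious difference | SE | Power |
|---|---|---|---|---|
| 100% | 5.00% | 0 | 0.01426 | 80% |
| 95% | 4.75% | 0.25 points | 0.01403 | 76% |
| 90% | 4.50% | 0.5 points | 0.01380 | 72% |
| 80% | 4.00% | 1.0 points | 0.01332 | 61% |

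True rates at the margin, 5% control and 9% TaTME:

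| Detection, control / TaTME | Observed difference | False non-inferiority |
|---|---|---|
| 100% / 100% | 4.0 points | 2.5% |
| 95% / 100% | 4.25 points | 1.7% |
| 90% / 100% | 4.5 points | 1.1% |
| 80% / 100% | 5.0 points | 0.4% |
| 100% / 90% | 3.1 points | 8.4% |
| 100% / 80% | 2.2 points | 21.9% |

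Example: at 100% / 90%, (0.04 − 0.031)/0.01556 − 1.96 = −1.38, and Φ(−1.38) ≈ 8.4%.

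The two directions are not mirror images. Lighter detection in the control arm costs power and makes a false claim less likely. Lighter detection in the TaTME arm makes a false claim more likely, and at the margin a 10% shortfall there removes 0.9 points (10% of 9%), against 0.5 points (10% of 5%) in the control arm.

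**The case against.** The strongest reply is that the protocol does not set up unequal follow-up. A reader might infer from 17.4 that TaTME patients are promised more frequent visits than controls. The sentence says frequent, not more frequent, and it stands in a benefit-risk paragraph. Neither schedule in section 12 is split by arm, and the conflict between 12.1 and the table touches both arms alike. That stands: differential follow-up is a possibility the wording leaves open, not a stated design feature.

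Second, every patient has a pelvic CT or MRI at three years, the time point of the primary endpoint, and a suspicious CT must be followed by MRI. This limits what visit frequency can do to a three-year percentage. It does not remove the problem. The table schedules no earlier pelvic imaging, so earlier detection rests on visits and discretionary examinations. Patients who die or are lost before three years never reach the scan. The log-rank test depends on when recurrence is detected, and the MRI rule acts only once suspicion exists.

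Third, a reader might take 13.2 to mean that a positive scan at any site counts as local recurrence. The section's heading and the definition in 3.3 exclude that; only the role of imaging against tissue is open.

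Fourth, a reader might conclude that sites alone decide the endpoint. The protocol plans central review of MRI and pathology and does not say that it has no part in the endpoint. Details of adjudication could sit in a document not shown here. The conflicts over schedule and definition, however, are fixed in this text.

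Finally, the detection fractions have no basis in the documents. That stands in full.

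**Conclusion.** The inconsistencies are real and bear on the primary endpoint: an arm-specific follow-up sentence that does not fit the common schedule, two schedules that differ by 3 against 7 visits by month 36, and a local recurrence definition without a combining rule, all in an open-label trial. They make arm-dependent detection possible. The documents do not show that it is intended or that it will occur, and the direction of any bias is unknown.

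The figures show sensitivity only. With about 53 expected events, 10% of the control events is fewer than two patients (0.10 × 18 = 1.8), and on the assumed fractions that shift alone moves power from 80% to 72%. The power losses and inflated error rates above should not be read as estimates for this trial: they rest wholly on assumed detection fractions and take no account of the common three-year scan. The point deserves correction because correction is cheap, with medium confidence as to its practical effect.

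**What to change.** 1. Reconcile the Follow-up paragraph of the trial summary, 12.1, the 12.3 table and 17.4, and state that the assessment schedule for local recurrence does not differ by arm. Which schedule applies is for the trial's clinicians; this review does not choose one.
2. Reconcile 13.2 with 13.1 and the definition in 3.3 by stating how site, imaging and histology or cytology combine for the primary event.
3. State that the central MRI and pathology review already planned confirms each reported local recurrence, with reviewers masked to allocation.

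The first two are changes of wording. The third asks sites to submit de-identified scans or reports, with allocation removed, for roughly 55 events. Events seen only on CT add a little review work, since the planned central review names MRI and pathology but not CT. None of the three calls for new examinations for the sake of the review.

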17.5 Compensation for injury

The VU University Medical Centre has an insurance which is in accordance with the legal requirements in the Netherlands (Article 7 WMO and the Measure regarding Compulsory Insurance for Clinical Research in Humans of 23th June 2003). This insurance provides cover for damage to research subjects through injury or death caused by the study.

1. € 650.000,-- (i.e. six hundred and fifty thousand Euro) for death or injury for each subject who participates in the Research;
2. € 5.000.000,-- (i.e. five million Euro) for death or injury for all subjects who participate in the Research;
3. € 7.500.000,-- (i.e. seven million and five hundred thousand Euro) for the total damage incurred by the organisation for all damage disclosed by scientific research for the Sponsor as 'verrichter' in the meaning of said Act in each year of insurance coverage.

The insurance applies to the damage that becomes apparent during the study or within 4 years after the end of the study.

19 APPENDICES

Appendix I: MRI protocol and staging definitions

Appendix II: Definition anastomotic leakage

Appendix III: Quality Assurance

Appendix IV: Pathology

APPENDIX I MR Imaging Protocol COLOR III

Hardware

1.5 / 3.0 T

External Phased Array Coil (no endorectal coil)

Patient Preparation

Spasmolytics may be used in cases where significant bowel movement artefacts are visible on the planning images, especially 3T

No endorectal filling or enema

Sequences and sequence angulation

Imaging should be performed according the ESGAR recommendations: Magnetic resonance imaging for the clinical management of rectal cancer patients: recommendations from the 2012 European Society of Gastrointestinal and Abdominal Radiology (ESGAR) consensus meeting. Eur Radiol (2013) 23:2522–2531

2D T2-weighted sequences

- sagittal and axial 2D T2-weighted sequence is mandatory for the assessment of tumour height, T-N-stage, MRF involvement and the presence of EMVI
- The use of a coronal 2D T2-weighted sequence is recommended
- axial and coronal T2-weighted sequence should be angulated perpendicular and parallel to the tumour axis for tumours in the middle part of the rectum
- For low rectal tumours, angulation depends on the extent of the tumour and may be performed perpendicular and parallel to either the tumour axis or the anal canal, or even both (4 series)
- Slice thickness: 3-4mm
- FOV: cranial border: upper side L5 / caudal border: beyond anal canal

Use of DWI is not obligatory for primary staging but is recommended for restaging (specifically for assessment of the T-stage) after CRT. B800-1000

No 3D T2-weighted and fatsuppressed sequences, T1-weighted sequence or contrast enhanced dynamic or steady state

T2 sequence (examples):

Siemens	Siemens	GE	Philips
TR > 6000 (8000-9000)	TR 4500	TR 4800	TR 5000-6000
TE 137	TE 128	TE 85	TE 135
Echotrain 61 (TSE)	Echotrain 25	Echotrain: 12	Echotrain
Acquisitions: 3	Acquisitions: 2-3	Acquisitions: 3	Acquisitions: 3
Slice thickness: 3-4mm	Slice thickness: 4	Slice thickness: 4	Slice thickness: 3
FOV: 240x 240	FOV: 240 x 240	FOV: 240 x 240	FOV: 240 x 240
Matrix 280 x 512	Matrix: 224 x 512	Matrix: 320 x 256	Matrix 320 x256meo
TR: shortest			
Matrix may vary per orientation			

Standard operating procedures regarding image quality

All participating sites will be asked to send a dummy run with the T2-weighted and diffusion-weighted images to check the image quality and parameters. The dummy run may be performed on a healthy volunteer or a patient with rectal cancer.

The dummy run will be checked on quality. The results will be send to the participating site.

MR staging

MR Images are judged on

- Position of tumour
 - o Distance to anal verge
 - o Length of internal sphincter complex
 - o Distance to the cranial border internal sphinctercomplex
 - o Extra low tumour: 0-2.0cm to anal verge
 - o Low tumour: 2.1-5.0cm to anal verge
 - o Mid tumour: 5.1-10.0cm to anal verge
 - o Location (anterior, right lateral, posterior, left lateral)
- Length of tumour
- Diameter of tumour
- T-status
 - o **T0**: no evidence of primary tumour
 - o **Tis**: carcinoma in situ: intraepithelial or invasion of lamina propria
 - o **T1**: tumour invades submucosa
 - o **T2**: tumour invades muscularis propria
 - o **T3a**: tumour invades beyond muscularis <1mm
 - o **T3b**: tumour invades beyond muscularis 1-5mm
 - o **T3c**: tumour invades beyond muscularis 5-15mm
 - o **T3d**: tumour invades beyond muscularis <15mm
 - o **T4a**: tumour invades directly into other organs or structures
 - o **T4b**: tumour perforates visceral peritoneum
- Distance to mesorectal fascia
 - o ≤ 1mm
 - o 1-2mm: mesorectal fascia at risk / threatened
- Extramural growth
 - o ≤ 5mm
 - o > 5mm
- EMVI: extramural vascular invasion
- N-status
 - o Malignant criteria:
 - Irregular borders
 - Round shape
 - Heterogenous signal intensity
 - o **N0**: no Lnn or Inn < 5mm without malignant criteria
 - o **N+**:
 - Lnn < 5mm with all malignant criteria
 - Lnn 5-9mm with ≥ 2 malignant criteria
 - Lnn ≥ 9mm (longest diameter)
 - o **N2**: at least 4 N+ Inn
- M- status if possible

